ICF	Informed Consent Form
JCRF	Joint Clinical Research Facility
NHS R&D	Nation Health Service Research & Development
PI	Principal Investigator
Participant	An individual who takes part in a clinical trial
REC	Research Ethics Committee
SAE	Serious Adverse Event
IBS	Irritable Bowel Syndrome
IBS-QOL	Irritable Bowel Syndrome Quality of Life (Questionnaire)

1 Introduction

Irritable Bowel Syndrome (IBS) is a very common gastrointestinal complaint causing abdominal pain associated with an abnormal bowel habit – either diarrhoea or constipation. Other symptoms may include flatulence, bloating and fatigue¹.

Many sufferers have food intolerances so that IBS frequently responds to restrictive diets^{2,3}. Similarly, enteral feeds lacking complex carbohydrate and long-chain triglycerides have been shown to be effective⁴. Such diets however, are not particularly appealing and can be socially disruptive. A treatment allowing patients to eat with minimal restriction would be widely welcomed.

It has become clear that the colonic microbiome in IBS is associated with abnormal overgrowth of facultative anaerobes, particularly members of the Enterobacteriaceae⁵. These organisms cause abnormal fermentation of food residues, leading to wind and discomfort⁶. Antibiotics are therefore sometimes useful⁵ but unfortunately, their effects are not long lasting. Reduction in the amount of food residue available for colonic microbial fermentation offers a novel and potentially exciting way of treatment. The expression of the major carbohydrate catalysing enzyme, amylase, has been shown to vary widely in otherwise healthy subjects⁷.

Enzyme-rich malt extract (ERME) is a by-product of the malting process. Customarily the enzymes generated by sprouting barley are destroyed by heat in the production of malt suitable for brewing. ERME is an extract taken before the enzymes are destroyed and it is rich in amylase, fructanases and glucanases. It is sweet, palatable and easily available at relatively low cost. ERME has been used as a foodstuff in baking and cookery for many years, and we have shown the enzymes of ERME still to be active in the equine gut⁸, where intrinsic levels of amylase are low

This product has now been launched as a food supplement (JUVIA) with the aim to improve symptoms of IBS by reducing food residues passing into the large intestine for fermentation.

In a preliminary study of patients with IBS, symptoms were reduced by ERME in 4 out of 5 patients with partial benefit in the fifth. This was associated with a dramatic reduction in hydrogen excretion on the breath, strong evidence of modified colonic fermentation.

IBS, however, is not a single condition¹. Several mechanisms produce the symptom complex apart from malfermentation. These include anxiety, constipation, (sometimes complicated by overflow diarrhoea) menstrual disturbances and musculo-skeletal problems. These can be separated by validated symptom analyses. We wish to know whether ERME is of any benefit in other IBS sub-groups⁸ and to seek biomarkers in urine and stool samples, which may allow objective identification of these groups, currently separable only by symptoms⁹. This study is designed to concentrate on the malfermentation form of IBS.

2 Patient Identification and Recruitment

This will be a single site study, conducted at the Joint Clinical Research Unit (JCRF),

Institute of Life Science 2, Swansea University, Swansea.

The research team will work with local Gastroenterologists and General Practitioners to identify potential subjects: Patients with a confirmed diagnosis of IBS made by a clinician and be aged between 18 – 65 years. They will also discuss with the IBS dietician group in respect of patients who may be considered for this study.

These potential subjects will be sent a Patient Information Sheet (PIS) and consent form in the post, together with a covering letter from either their local GP or the Consultant Gastroenterologist (whoever is the most appropriate i.e. who has provisionally identified them as suitable for the study). The Information Sheet will contain the contact details of the research team at JCRF and ask patients to get in touch if they would like to know more about the study.

With permission from the Research Ethics Committee to do so, the research team may telephone recipients of the patient information sheet to see whether they have any questions about the study and whether they might be interested in taking part.

Initial Screening by telephone

For any patient who may be interested in taking part, the research team will undertake initial 'screening' over the telephone if this is acceptable to the patient. The purpose of this would be to avoid patients traveling to the hospital unnecessarily (if they do not meet the inclusion criteria).

A Case Record File will document the research team's telephone 'screening' conversation with the patient. This will commence with a check that the patient has received the PIS and is happy to answer some initial screening questions over the telephone.

Patients will be asked to complete two questionnaires over the telephone, appendix 1 (Rome IV) to assess current symptoms of IBS (Both abdominal pain and altered bowel habit), and Questionnaire (Appendix 2) to confirm malfermentation. If the responses deem them suitable for inclusion and they have none of the exclusion criteria they will be invited to attend a research appointment at the JCRF. Where there is doubt as to a patient's potential eligibility the CI/PI will be asked for a view before the patient is invited for an appointment.

Patients will be asked to bring a urine and stool sample to the screening visit. The research team will post collection kits to the patient in advance with information on collection of the sample. The stool sample will be processed by Microba Laboratory in Brisbane, Australia and the urine sample will be analysed by [name] at Brunel University, Uxbridge. Chain of custody and storage will be maintained as required for the samples. Stool sample collection is easy, just requires a smear of stool sample from toilet paper onto a swab, and then placed in a pouch sealed and brought into the clinic. The sample does not go in the fridge but stays at room temperature until they attend clinic and it will be frozen at -20 for subsequent batch dispatch to the laboratory.

Research Clinic Visit

On arrival at clinic, the research nurse will confirm that the patient has received the PIS and discuss the study with the patient. The research nurse will answer any initial questions that the patient may have and confirm eligibility criteria.

At this clinical appointment and the eligibility, criteria discussed previously by telephone will be confirmed during this appointment.

We plan to recruit at least 20 subjects who complete the study. In case of dropouts, we would plan to recruit up to 30 subjects to accommodate subjects that withdraw or are lost to follow up.

Inclusion Criteria:

1. Aged 18-65
2. Current symptoms of IBS (abdominal pain and altered bowel habit) ROME IV criteria
3. Prepared to take ERME (JUVIA) for duration (taste test available for patient)
4. Normal full blood count within last 12 months (from medical notes if available)
5. Previous Calprotectin (from medical notes if available) <80.ug/g
6. Previous tTG (Tissue Transglutaminase) (from medical notes if available)
7. Positive for malfermentation as decided by IBS Questionnaire Score
8. Registered with a GP and consent to GP being informed

Exclusion Criteria:

1. Pregnant, planning to become pregnant or lactating
2. Diabetic (or other co-morbidity which the CI considers inappropriate)
3. On a restrictive diet or unwilling or unable to change diet
4. Current medication (e.g. opiates) that may influence bowel symptoms (at discretion of the CI)
5. Antibiotics in the previous 6 weeks
6. Other gastrointestinal disease (e.g. coeliac, Crohn's disease or Ulcerative colitis)

-
7. Significant gastrointestinal surgery (this will be a clinical decision and any patient who has had a surgical procedure that would change the mechanics of gut function would be excluded)
-
8. Involved in other gastroenterology research project or other interventional study that would affect results
-

Patients who do not meet the entry criteria will not be enrolled into the study, but will attend their routine clinic appointments and or general practitioner care. Patients who meet the inclusion criteria and would like to take part will have eligibility confirmed by the local investigator who will also take informed consent or delegate to the research nurse **Note:** The research team will offer the patient an opportunity to taste the product before enrolling so that they can assess whether they will be able to take the product daily for the 4-week period required.

3 Study Procedures

1. Following telephone screening, informed consent and enrolment, patients will be asked to complete the IBS Severity Score (appendix 3) and IBS Quality of Life Questionnaire (appendix 4). Additionally they will be asked to complete the Nijmegen anxiety questionnaire (appendix 5) & the Cambridge IBS type questionnaire. Demographic data will be collected as per the clinical record form as described in the patient information sheet.
2. Where a patient does not have a faecal calprotectin (FC) result, a test may be requested if the investigator feels it is necessary.
3. A urine sample will be collected at baseline and frozen to be sent to [name], Brunel University Uxbridge for determination of bacterial metabolites by SIFT/MS (specific ion flow tube mass spectrometry). A faecal sample will also be collected and stored prior to sending to Microba in Brisbane, Australia and again at week 4 for microbial analysis.
4. ERME (labelled as JUVIA) a total of 40mls daily (to be taken with meals) Subjects will be supplied with 3 x 450ml containers of JUVIA. Muntons Maltsters of Stowmarket Suffolk will supply the product to our current packers Chyialis Creation house [name]. On receipt of the product from the supplier details will be entered onto an accountability log at JCRF, and stored appropriately. The product will be stored by the research team in a cool (<25 degrees C), dry and secure environment.
5. The participants will be given enough product (JUVIA) to last for 4 weeks and instructed how to take the product with food daily (20mls at breakfast and 20mls with last meal of the day).
6. Patients will be provided with information as to how to store the product at home and asked to contact the team if they have any concerns.
7. Participants will be asked to complete the IBS severity score questionnaire and IBS Quality of Life Questionnaire at 2 weeks and 4 weeks post their first research hospital appointment. A member of the research team will telephone the patient to remind them to do this and, if preferred, can complete the 2-week questionnaires with the patient over the telephone. Week 4 will be undertaken when they attend the final clinic visit.
8. Patients will be made aware that due to the effects of JUVIA, they may

experience bacterial 'die-offs' when essential nutrients for these bacteria are no longer available in the gut, where symptoms are exacerbated during the first few days and encouraged to continue as symptoms will settle.

9. At 4 weeks post Visit 1, a final hospital (Visit 2) will take place and the same procedures undertaken at Visit 1 will be repeated. A further faecal and urine sample will be collected and urine again frozen prior to transporting to the laboratory for analysis.
10. IBS severity score, IBS QoL questionnaires, Nijmegen and will again be completed at week 4 and the patient will be weighed.

4 Adverse Events and Patient withdrawal

1. It is unlikely that malt extract, which is already widely used in the food industry, will cause any major difficulties or unwanted effects. In the unlikely event that the patient becomes ill while participating in the study they must report this to the Research team at JCRF, Swansea Bay University Health Board who will discuss with the Chief Investigator/Principal investigator whether or not the participant should be withdrawn from the study.

Adverse events will be collected by asking patients about their symptoms during enrolment in the study. The adverse event will be recorded and reported following the Sponsor's normal procedures.

In the event of a Serious Adverse Event in a patient taking part in the study, the Sponsor's normal reporting procedures apply.

Should the participant find the product unpalatable or unacceptable, they will be asked to remain in study follow-up if they are prepared to do so. If a patient stops taking the product then this must be recorded, along with the reason why. Where patients are agreeable the research team will follow up with them 2 weeks after stopping the product and patients will be asked for permission to use the data and samples already collected to that point, together with any subsequent follow-up data.

If the participants wish to withdraw at any point during the study for whatever reason, they will be asked to remain in follow-up and to allow any data and/or samples collected to that point to be included in the analysis. Participants are free to withdraw without prejudicing their future care and details of withdrawal will document in the Case Record Form.

5 Treatment preparations

ERME (Enzyme rich malt extract) – JUVIA – marketed food supplement. 450mls per bottle

40 mls daily JUVIA provided by Muntons, maltsters of Stowmarket and repacked by Chrysalis. Each subject will be given 2 bottles of JUVIA.

6 Samples

Stool Analysis plan

Faecal samples will be stored before being sent as a batch to Microba Brisbane,

Australia for genomic assay using the Shotgun technique for analysis of the microbiome and comparison with their extensive data collection. Microba have developed and validated a method of faecal sampling which involves taking a smear from lavatory paper and storing it in a specially developed container. Full chain of custody will be maintained.

Urine sample

These will be frozen and stored and sent as a batch to [name] at Brunel University, London for subsequent Flow tube/Mass spectrometry (SIFT/MS) analysis.

Sample identification, Storage and destruction

All samples will have a unique research number ensuring the laboratory analysing samples have no information about participants or can identify them in any way. Samples once analysed will be destroyed in accordance with regulatory practice.

7 Safety Reporting

There not expected to be any safety issues however all Adverse Events (AE) will be documented in line with details in Appendix 6 “Safety Reporting in Non-CTIMP Research.

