Any protocol deviations will be categorized as ‘major’ or ‘minor’, listed, and summarized. All subjects will be given a unique patient identifier number at time on consent which will be used to record all data on the CRF and study database. This ensures patient confidentiality and only staff involved in the study will have access to this database. The database will be shared with the study statistician, who will not have any linked patient identifiers.

The sponsor company representative will be given access to relevant patient information for the purpose of study monitoring to ensure the study and subjects have been recruited and managed in accordance with the protocol and REC approval.

9 Efficacy analysis

Summary statistics will be presented for each efficacy endpoint at baseline, two and four and for the change from baseline at two and four weeks.

10 Safety analysis

The incidence, nature, severity, relatedness, duration, outcome, seriousness and expectedness of treatment emergent adverse events will be listed and tabulated. Reporting of events will be as outlined in Appendix 6.

11 Exploratory analysis

This may include but not limited to:

- Analyzing completing subjects only, repeating parametric analyses using non-parametric analyses, analyzing using a longitudinal model, and investigating different methodologies for adjusting for missing values.

12 Funding

The study will be funded by Ateria Health Ltd. As the sponsor, they have confirmed patient indemnity with CAN Insurance Co. Ltd. For £5,000,000.

13 Reporting and Publication

A final report will be completed and either a full report or summary will be submitted to the REC and R&D after perusal and consent from the Sponsor.

It is intended to publish the results whether positive or negative, in both abstracts and major gastroenterological journals.

14 References

1. Forbes AL Hunter J O Irritable Bowel Syndrome *Medicine* 35 267-271 2007
3. Editorial: balancing fibre and FODMAPs in IBS - a 'rye' look at an old problem. Quigley EM. *Aliment Pharmacol Ther.* 2016 Nov;44(10):1134-1135. doi: 10.1111/apt.13805.

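### Follow-up after the product stops is uneven: conditional for early stoppers, not stated for completers, and unclear for participants withdrawn through illness

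*Protocol*

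**What the plan says.** **Endpoints.** The safety endpoints in the Protocol's General statistical considerations include duration and outcome. Section 10 (Safety analysis) repeats them: "The incidence, nature, severity, relatedness, duration, outcome, seriousness and expectedness of treatment emergent adverse events will be listed and tabulated".

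**Collection.** Section 4: "Adverse events will be collected by asking patients about their symptoms during enrolment in the study". The text shown gives no date on which enrolment, or adverse event collection, ends. Appendix 6 expects the protocol to define the end of the study, and no definition appears in the text shown.

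**Completers.** Section 3 item 5: "The participants will be given enough product (JUVIA) to last for 4 weeks". Section 3 item 9: "At 4 weeks post Visit 1, a final hospital (Visit 2) will take place". No later contact is stated.

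**Early stoppers.** Section 4 says of a participant who dislikes or cannot accept the product that "they will be asked to remain in study follow-up if they are prepared to do so". It continues in general terms: "If a patient stops taking the product then this must be recorded, along with the reason why". The 2-week contact follows directly: "Where patients are agreeable the research team will follow up with them 2 weeks after stopping the product". Participants who choose to withdraw are also asked to stay in follow-up.

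**Illness.** Under section 4 item 1, the research team discusses with the chief or principal investigator "whether or not the participant should be withdrawn from the study". That sentence says nothing about follow-up.

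**Missing data.** Missing efficacy data are handled by last observation carried forward (LOCF). The severity score is collected at baseline, week 2 and week 4 (section 3 items 1, 7 and 10).

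**The concern.** The protocol sees value in a contact 2 weeks after the product stops, but places it only in the early-stopping paragraph. For completers, the planned end of product and the last planned contact fall together, so an event open that day is not followed to its end and an event starting afterwards is not seen.

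For illness, the decision is framed as leaving the study rather than as stopping the product. The two groups expressly asked to remain in follow-up are those who find the product unacceptable and those who choose to withdraw. A participant withdrawn by the investigator through illness is not expressly in either group. Site staff could reasonably end data collection there. That would lose the event outcome and the week-4 severity score in a participant whose data bear most on tolerability. The case is foreseeable: section 3 item 8 warns that symptoms may worsen in the first few days.

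**Working it through.** The protocol states no figure for this point, so there is none to reproduce. The check sets out the contact timeline and its consequences.

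**Step 1. Planned observation off product.** Inputs: product for 28 days and Visit 2 on day 28 (section 3 items 5 and 9); contact 14 days after early stopping, if agreed (section 4). Off-product observation = day of last contact minus day product stops.

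| Participant | Last contact | Days off product observed |
|---|---|---|
| Completer, full 28 days of product | day 28 | 28 − 28 = 0 |
| Stops day 7, 2-week contact only | day 21 | 14 |
| Stops day 7, also stays to week 4 | day 28 | 21 |
| Stops day 14 | day 28 | 14 |
| Stops day 21 | day 35 | 14 |
| Stops early and declines follow-up | at stopping | 0 |
| Withdrawn by investigator through illness | not specified | 14 if the general stopping clause applies and the participant agrees |

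For a stop on day t with follow-up to week 4 as well, the figure is max(14, 28 − t). The 2 weeks are therefore neither guaranteed nor a cap.

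**Step 2. When product actually stops.** At 40 ml daily (section 3 item 4), 28 days need 28 × 40 = 1,120 ml.
- Section 3 item 4 supplies three 450 ml bottles: 1,350 / 40 = 33.75 days, up to 33.75 − 28 = 5.75 days beyond Visit 2.
- Section 5 supplies two: 900 / 40 = 22.5 days, which run out 28 − 22.5 = 5.5 days before Visit 2.

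The zero for completers in Step 1 thus assumes exactly 4 weeks of product. The two passages contradict each other and must be reconciled.

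**Step 3. Events still open at Visit 2 (illustration only).** The protocol gives neither onset times nor durations. Assuming onset uniform over 28 days and every event lasting d days, the share open on day 28 is d / 28.
- d = 5: 5/28 = 17.9%.
- d = 10: 10/28 = 35.7%.
- Early onset instead: an event starting by day 7 and lasting 10 days closes by day 17, so the share open is 0%.

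The share thus runs from 0% to about 36% across these assumptions. For the early exacerbation that section 3 item 8 expects, the low end is the more natural reading.

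**Step 4. Effect on the primary endpoint.** A participant who leaves before week 2 has only the baseline score, so LOCF gives a week-4 change of 0. One who leaves between weeks 2 and 4 has the week-2 score carried forward. With 20 analysed (section 2 plans at least 20 completing), one participant is 1/20 = 5% of the data. If the other 19 have mean change m, one imputed zero makes the mean 19m/20 = 0.95m. Whether this is too favourable or too cautious depends on the true score, which would not be known.

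**The case against.** **The general stopping clause may already cover illness.** It is not limited to taste: it refers to any patient who stops the product, and the 2-week contact follows it. This stands. A reader might infer that ill participants are certain to lose follow-up. The documents do not support that; they leave it unclear.

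**Duration and outcome can mostly be determined.** This also stands. Events resolved by week 4 are fully known, and events open at last contact can be listed as ongoing with censored duration. A reader might infer that these endpoints cannot be determined, but only events open at, or starting after, last contact are affected.

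**Incidence windows are not clearly mixed.** A reader might infer that early stoppers are watched longer than completers. Someone stopping on day t is contacted on day t + 14, so only a stop after day 14 carries observation past day 28. Nor does the text say that this contact extends adverse event collection.

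**Other documents may fill the gap.** A statistical analysis plan may define treatment-emergent events and the handling of open ones, and the sponsor's procedures, cited in section 4 for recording and reporting, may cover follow-up. This stands in part. An analysis plan can set a censoring rule but cannot create a patient contact. Section 7 refers adverse events to Appendix 6, whose table sets reporting deadlines and has nothing on following events to resolution.

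**A later contact for completers is a design preference.** No passage promises one, and this is a pilot of a marketed food supplement. That limits the weight of the point. It does not remove the mismatch between named duration and outcome endpoints and a last contact that coincides with the planned end of product.

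**Conclusion.** The point holds as an unevenness and an ambiguity in follow-up. Early stoppers who agree have a contact at 14 days, completers have none stated after Visit 2, and the position after investigator-led withdrawal through illness is not settled by the text.

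The consequences are censored duration and unknown outcome for events open at last contact, no sight of later events, and LOCF in place of an ill participant's week-4 score if that participant leaves the study. At 20 participants, each such case is 5% of the primary analysis.

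The zero days for completers assumes exactly 28 days of product, which the bottle counts put in doubt. The 18% and 36% hold only under uniform onset with assumed durations, and fall to zero in the early-onset example. The low expected risk and pilot design keep this at a change worth making because it is cheap, not a defect that invalidates the study.

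**What to change.** 1. In section 4 item 1, separate stopping the product from leaving the study. State that anyone who stops the product for any reason, including illness or an investigator decision, is asked to remain in follow-up for the week-4 questionnaires and for adverse event outcome. This extends a request the protocol already makes of others. Whether to stop the product stays with the investigator.
2. Apply the existing 2-week post-product contact to completers by telephone, asking about new events and the outcome of open ones. At minimum, do this for those with an event open at Visit 2.
3. State when adverse event collection ends, and define the end of the study as Appendix 6 expects.
4. Reconcile the bottle numbers in section 3 item 4 and section 5, since they bear on when product actually stops.

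The cost is protocol wording and 20 to 30 short calls by a team that already telephones participants at week 2 (section 3 item 7). The downside is a last contact about 2 weeks later.

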8.4 Record Retention

The investigator will maintain confidential all study documentation, and take measures to prevent accidental or premature destruction of these documents.

The documents will be retained in accordance with regulatory guidelines and those of its institution. Records will be stored in the JCRF, prior to off-site storage at a long-term storage facility.

The Investigator will notify the Sponsor prior to destroying any study essential documents following the Clinical Trial completion or discontinuation.

9 General statistical considerations

All baseline, disposition, protocol compliance, exposure and outcome variables (efficacy, safety and exploratory) will be listed and summarized.

The standard summary statistics for continuous baseline and outcome variable are N.mean, standard deviation, median, quartiles, minimum and maximum. The standard summary statistics for categorical baseline and outcome variable are: count and proportion (expressed as percentage).

Sample size calculation

No formal sample size has been calculated for this pilot study.

Endpoints

Primary Efficacy Endpoints

The primary endpoint is the change in IBS severity score from baseline (visit 1) to four weeks (visit 2).

Secondary Efficacy Endpoints

The secondary efficacy endpoints comprise the change in IBS severity score from baseline at two and four weeks will include:

- 1 Severity of abdominal pain
- 2 Frequency of abdominal pain
- 3 Change in abdominal bloating
- 4 Change in bowel habit "satisfaction"
- 5 Change in impact of IBS upon lifestyle
- 6 Change in bowel frequency
- 7 Change in stool consistency
- 8 Change in absence from work days related to IBS (as defined by IBS severity score scales)
- 9 Change in IBS QoL Questionnaire Scores.

Safety Endpoints

The safety endpoints are the incidence, nature, severity, relatedness, duration,

outcome, seriousness and expectedness of treatment emergent adverse events.

Missing Data

Subjects with missing efficacy data will be analysed on a last-observation-carried-forward basis.

8 Study conduct

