Appendix 3: completed at clinic visit 1,2 weeks, 4 weeks

IB patient severity score completed 3 times during the course of the study

IBS QUESTIONNAIRE

Name: _____ G.P. Name: _____
 Address: _____ Address: _____
 Telephone: _____ Telephone: _____
 Date of birth: _____

Marital status: Single / Married / Divorced / Widowed / Co-Habit
 Occupation: _____ Sex: M F

Ethnic background: Caucasian (white) / Afro-Caribbean / Asian / Oriental
 Fathers Occupation (even if retired): _____

INSTRUCTIONS

This form is designed to enable us to record and monitor the severity of your IBS. It is to be expected that your symptoms might vary over time, so please try and answer the questions based on how you currently feel (ie over the last 10 days or so). All information will be kept in **strict** confidence.

- For questions where a number of different responses are a possibility please circle the response appropriate to you.
- Some questions will require you to write in an appropriate response.
- Some questions require you to put a cross on a line which enables us to judge the severity of a particular problem.

For example:

How severe was your pain?

Please place your cross (X) anywhere on the line between 0-100% in order to indicate as accurately as possible the severity of your symptom.
 This example shows a severity of approximately 90%.

1

PART 1 : SEVERITY SCORE

- Do you currently suffer from abdominal (tummy) pain? YES NO
Circle appropriate box
 - If yes, how severe is your abdominal (tummy) pain?
 - Please enter the number of days that you get the pain in every 10 days.
 For example if you enter 4 it means that you get pain 4 out of 10 days. If you get pain every day enter 10
 Number of days with pain x10
- Do you currently suffer from abdominal distension* (bloating, swollen or tight tummy) YES NO
(*women, please ignore distension related to your periods) Circle appropriate box
 - If yes, how severe is your abdominal distension/tightness
- How satisfied are you with your bowel habit?
- Please indicate with a cross on the line below how much your Irritable Bowel Syndrome is affecting or interfering with your life in general

IBS SEVERITY SCORE:

2

For office use only
SCORE

IB patient severity score completed 3 times during the course of the study

PART 2 : OTHER IBS DATA

BOWEL HABIT

5. a) What is the most number of times you open your bowels per day/week/month?

Number of times per day / week / month (Circle appropriate)

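### Section 5 issues two bottles per subject where Section 3 issues three; two bottles cover only 22.5 of the 28 treatment days

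*Protocol*

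**What the plan says.** The amount of product issued to each subject appears twice in the protocol, with different numbers.

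- Section 3 (Study Procedures), item 4: "Subjects will be supplied with 3 x 450ml containers of JUVIA".
- Section 5 (Treatment preparations): "Each subject will be given 2 bottles of JUVIA".

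The other inputs agree. Both sections give 450 ml per container and 40 ml per day. Section 3 item 5 splits the dose as "20mls at breakfast and 20mls with last meal of the day" and sets a supply requirement: "The participants will be given enough product (JUVIA) to last for 4 weeks". The note after the exclusion criteria in Section 2 says that subjects must be able to "take the product daily for the 4-week period required".

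Three measurements fall at the end of treatment. Under the heading Primary Efficacy Endpoints, the primary endpoint is the change in severity score between Visit 1 and Visit 2 at four weeks. The severity form in Appendix 3 asks for answers "based on how you currently feel (ie over the last 10 days or so"). Section 3 item 9 adds that at Visit 2 "A further faecal and urine sample will be collected".

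**The concern.** The two statements cannot both describe what a subject receives. Because dose, bottle size and duration are all fixed, the protocol's own figures show which is right, and two bottles do not last four weeks.

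The number of bottles determines whether subjects are still on treatment when the outcome is measured. If the site issued two bottles and nothing more, even a perfectly compliant subject would run out before Visit 2. The week-4 severity score, which is the primary endpoint, would then partly describe a period off product, and the only post-baseline stool and urine samples would be taken off product. The protocol describes no second issue: the week-2 contact is a telephone call about questionnaires, and the only later clinic visit is the final one.

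**Working it through.** **Inputs**

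| Input | Value | Place in protocol |
|---|---|---|
| Daily dose | 40 ml (20 ml twice) | Section 3 items 4 and 5; Section 5 |
| Bottle | 450 ml | Section 3 item 4; Section 5 |
| Duration | 4 weeks = 28 days | Section 2 note; Section 3 items 5 and 9 |
| Bottles per subject | 3 | Section 3 item 4 |
| Bottles per subject | 2 | Section 5 |

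**Need**

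Volume = daily dose × days = 40 × 28 = 1120 ml. In servings of 20 ml, 1120 / 20 = 56.

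Whole bottles needed = 1120 / 450 = 2.49, rounded up to 3. The Section 5 figure of 2 is not reproduced; the Section 3 figure of 3 is.

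**What each stated supply covers** (days = bottles × 450 / 40)

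| | Two bottles (Section 5) | Three bottles (Section 3) |
|---|---|---|
| Volume | 900 ml | 1350 ml |
| Servings | 45 | 67.5 |
| Days covered | 22.5 | 33.75 |
| Against 1120 ml | 220 ml short | 230 ml spare |
| In days | 5.5 short | 5.75 spare |
| In servings | 11 of 56 short | 11.5 spare |

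The shortfall is 220 / 1120 = 19.6% of the need.

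**Which measurements are exposed**

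Week 2 needs 40 × 14 = 560 ml, which 900 ml covers with 340 ml left. The week-2 scores are not affected.

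For week 4, take Visit 1 as day 0, Visit 2 as day 28 and full compliance. The protocol does not fix the first dose, so two cases are shown.

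- First dose at the last meal of day 0: one serving that day plus 44 on days 1 to 22 makes 45, so the supply ends with the last meal of day 22. Missed servings are 10 on days 23 to 27 plus breakfast on day 28, which is 11 (about 5.5 days).
- First dose at breakfast on day 1: 44 servings on days 1 to 22 plus breakfast on day 23 makes 45. Missed servings are one on day 23, eight on days 24 to 27 and breakfast on day 28, which is 10 (about 5 days).

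Against a recall period of about 10 days, 5 to 5.5 days is roughly half. This is approximate, since the form itself gives the period only loosely.

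**The case against.** The strongest reply accepts the contradiction and the arithmetic but says that the matter is editorial. Section 3 is the operative procedures section. It gives an adequate number and, separately, requires a four-week supply, so staff following either item would issue enough. Section 5 is a short product description. A shortage would also be hard to miss: subjects are invited to contact the team with concerns, the team telephones around week 2 when about 340 ml (8.5 days) would remain, and any stopping of product must be recorded with its reason. Finally, the study is a pilot with no formal sample size and a descriptive efficacy analysis, so no success threshold could be tipped by a few days off product.

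Much of this stands as a limit on the consequences. Harm is conditional on issue by Section 5, and an unnoticed shortfall across the whole study is not the likeliest outcome. It is also right that half of the recall period is not half of the score: within the severity part of the form only the pain-days item counts days out of ten, and the other items are ratings of the present state.

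It does not rescue the number. None of those contacts is a resupply rule, and recording a stop does not put the subject back on product. Section 5 is headed as the place where treatment preparations are set out, so staff may reasonably look there for the quantity. A descriptive pilot still reports the week-4 change as its main result.

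**Conclusion.** The point holds. Section 5 is wrong as written and Section 3 item 4 is right, because three is the smallest whole number of bottles that meets the stated dose and duration. Two bottles leave a subject 220 ml short, which is 5.5 of 28 days of product.

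The consequence rests on three assumptions: product is issued by Section 5 without resupply, the subject takes every dose, and Visit 2 falls on day 28. Under these, the last 5 to 5.5 days before the primary endpoint and the final samples are off product. Neither the size nor the direction of any bias can be given, because the documents do not say how long an effect persists after stopping. If the site issues by Section 3, nothing is lost. The error should be corrected, but it does not undermine the design.

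**What to change.** In Section 5, replace the two bottles with three bottles of 450 ml, so that it matches Section 3 item 4. Dose, duration, endpoints and analysis stay as they are.

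The cost is one number in one sentence. In product it is at most one extra bottle per subject: 30 × (3 − 2) = 30 bottles for the planned maximum of 30 subjects, and none if the site already issues three.
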